Donor Iron Deficiency Study

Protocol Version 2.5 – December 6, 2019

Study Sponsor: National Heart, Lung, and Blood Institute

Grant: NIH R01-HL133049

A randomized trial to determine if RBCs from donors with iron deficient erythropoiesis have decreased post-transfusion RBC recovery and whether iron repletion improves recovery

ClinicalTrials.gov #NCT02889133

Concept Synopsis and Study Schema

Each year, ~5 million regular donors meet almost half the transfusion needs of the United States by voluntarily donating their blood. Despite fulfilling all requirements for blood donation, almost two-thirds of the women and half of the men who are regular blood donors are iron deficient. In order to manage the inventory, red blood cell (RBC) units destined for transfusion can be stored for up to 42 days prior to transfusion based on FDA guidelines. This guideline is based on a post-transfusion recovery study in which one must prove to the FDA that, on average, using healthy volunteers, more than 75% of transfused red cells remain in circulation for 24 hours at outdate. **This research will determine if RBC units from iron-deficient volunteer blood donors fail to meet U.S. FDA standards for 24-hour post-transfusion recovery.** RBCs from iron-deficient donors may be specifically damaged by refrigerated storage. In studies with a mouse model of iron deficiency (with hemoglobin levels similar to those that are acceptable for human blood donation), we found a mean 10.6% further decrease in the 24-hour post-transfusion recovery of refrigerator-stored red cells from iron-deficient animals, as compared to the post-transfusion recovery from iron-replete littermates. A comparable decrement in post-transfusion recovery of refrigerator-stored red cells from iron-deficient human volunteer blood donors would result in many of these units failing to meet established quality standards for clinical use. This study will also test whether giving iron deficient donors their iron back will improve the quality of their red cells during refrigerator storage.

Research Question(s)/Hypothesis(es):

Primary

1. The 24-hour post-transfusion RBC recovery from units obtained from iron-deficient donors will not meet FDA standards for clinical use.
2. The 24-hour post-transfusion RBC recovery from units obtained after intravenous iron repletion will improve significantly and will meet FDA standards for clinical use.

Secondary

1. Iron therapy will improve neurocognition and emotional well-being in donors with iron deficient erythropoiesis.
2. Metabolite levels in the transfusate will be associated with 24-hour post-transfusion RBC recovery and iron status.

Study Schema:

This is a randomized, controlled, double-blind clinical trial. 60 healthy regular donors who meet donation standards, while exhibiting iron-deficient erythropoiesis by laboratory test criteria, will donate a single standard RBC unit that will be leukoreduced and stored under standard conditions for 42 days. The FDA gold standard measure for the quality of RBCs destined for transfusion is the 51Cr-radiolabeled 24-hour RBC recovery study. Thus, a small aliquot of the transfused RBCs will be radiolabeled and injected into the volunteers on day 41 or 42 of storage. RBC recovery will be calculated from samples obtained at 5min, 7.5min, 10min, 12.5min, 15min, 30-minutes, 1-hour and 24 hours after autologous infusion as per the standardized protocol.⁴ For secondary outcomes, study surveys and neurocognitive assessments to assess symptoms of anemia and iron deficiency will also be performed prior to donation and prior to infusion.

In a prospective, randomized, double-blind manner, these donors will then receive either intravenous saline or low-molecular weight iron dextran (or ferric carboxymaltose if iron dextran is unavailable due to supply) within 1-day to 4-weeks after the first post-transfusion recovery study. After five months, they will donate a second RBC unit, similarly stored for 42 days, and autologous 51-chromium 24-hour post-transfusion RBC recoveries will again be determined. The primary outcome will be the group mean difference in 24-hour post-transfusion recovery difference from after treatment to baseline, between the groups receiving intravenous saline and iron.

[figure not shown]

TABLE OF CONTENTS

1. Background and Significance.....	7
2. Objectives	
2.1. Primary Hypothesis.....	11
2.2. Secondary Hypothesis.....	11
3. Study Population	
3.1. Enrollment Inclusion criteria.....	11
3.2. Enrollment Exclusion criteria.....	12
4. Trial Enrollment	
4.1. Screening / Recruitment.....	12
4.2. Randomization.....	13
4.3. Blinding.....	14
5. Interventions	
5.1. Blood donation.....	15
5.2. Chromium-51 post-transfusion RBC recovery	15
5.3. Total Dose Iron Infusion.....	16
5.4. Cognitive and Emotional Status Assessment.....	18
5.4.1. Cognition.....	18
5.4.2. Emotion.....	20
5.4.3. Hearing.....	20

Serum ferritin and RBC zinc protoporphyrin detect iron-deficient erythropoiesis in volunteer blood donors. Iron deficiency, a decrease in the amount of body iron, is detected clinically by measuring indicators of iron storage (e.g., serum ferritin), and of iron supply (e.g., RBC zinc protoporphyrin). In the absence of complicating factors, as iron stores decrease, serum ferritin levels decline; a serum ferritin level less than 12 $\mu\text{g}/\text{L}$ is virtually diagnostic of the absence of marrow iron stores. RBC zinc protoporphyrin monitors the supply of iron available for RBC production. In the developing RBC, the insertion of iron into protoporphyrin IX is the final step in producing heme for incorporation into hemoglobin. If iron is unavailable, divalent zinc is incorporated instead, producing zinc protoporphyrin, which binds to hemoglobin and persists for the life of the RBC as a biochemical indicator of an inadequate supply of iron for RBC production.^{1,3}

Four successive stages of iron deficiency can be distinguished (Fig. 2). **Reduced iron stores (not shown):** As iron stores decrease, serum ferritin levels decline proportionally. **Iron depletion:** Iron depletion develops when iron stores are absent, but iron delivery to the erythroid marrow for producing hemoglobin and other functional iron compounds is maintained by the combination of iron recycling from senescent RBCs and gastrointestinal iron absorption. With absent iron stores, the serum ferritin falls to $<15 \mu\text{g}/\text{L}$. Because the iron supply for RBC production is maintained, RBC zinc

protoporphyrin levels remain in the reference range. **Iron-deficient erythropoiesis:** With further reductions in body iron, the lack of iron limits production of hemoglobin and other iron-requiring compounds, resulting in iron-deficient erythropoiesis. Nonetheless, the effect on the circulating hemoglobin concentration is insufficient to be detected by the standards used to screen blood donors, which currently only includes a hemoglobin test. As newly formed RBCs replace senescent RBCs, RBC zinc protoporphyrin progressively increases, providing an index reflecting the severity and duration of the inadequate supply of iron for erythropoiesis. Further decreases in the nominal serum ferritin levels have no physiological meaning. Thus, **the combination of a serum ferritin <15 µg/L and an increased RBC zinc protoporphyrin (i.e., >80 µmol/mol heme), is highly specific for iron-deficient erythropoiesis.**^{1,3}

Iron-deficiency anemia: Further diminution in body iron produces frank iron-deficiency anemia, which would result in donor deferral.

Iron deficiency is common in volunteer blood donors. In the United States in 2011, of the donors who provided the ~15.7 million units of RBCs that were collected, 69% were repeat donors.⁵ In addition, in Canada, ~90% of RBC units collected for transfusion are provided by repeat donors.⁶ Although iron deficiency is surprisingly prevalent in first-time donors,^{7,8} its prevalence is even higher in the particularly altruistic frequent donors, especially among women of childbearing age.^{9,10} In the REDS-II Donor Iron Status Evaluation (RISE) study,¹¹ up to 49% and 66% of male and female frequent donors, respectively, manifested either iron depletion (i.e., absent iron stores) or iron-deficient erythropoiesis. Similar frequencies of iron deficiency were also reported in Canadian,⁶ Austrian,¹² Danish,¹³ and Dutch¹⁴ populations.

RBCs from donors with iron-deficient

[figure not shown]

[figure not shown]
Figure 2. RBC zinc protoporphyrin progressively increases with increasing severity of iron deficiency. Iron deficiency progresses from reduced iron stores to iron depletion, in which there is normal erythropoiesis with normal zinc protoporphyrin levels, but decreased ferritin due to absent iron stores. The next stage is iron-deficient erythropoiesis, in which increased RBC levels of zinc protoporphyrin and very low serum ferritin levels reflect both absent iron stores and the lack of sufficient iron for normal hemoglobin production. As iron deficiency progresses further, frank iron deficiency anemia develops with insufficient iron for maintaining adequate hemoglobin levels. **Our target population is human donors with iron-deficient erythropoiesis.** Adapted from Hastka et al.¹ and Brittenham³.

erythropoiesis have impaired tolerance for refrigerated storage and decreased post-transfusion RBC recovery. RBCs from individuals with iron deficiency anemia have decreased levels of endogenous antioxidants,^{15,16} have evidence of oxidative damage,^{17,18} and are more sensitive to oxidative stress^{15,18} and low pH;¹⁶ the latter decreases progressively during RBC storage.¹⁹ Furthermore, refrigerated storage induces oxidative stress in donor RBCs and inhibits their oxidative stress defense mechanisms.^{17,20-24} Oxidative damage *per se* also impairs RBC deformability²⁵ and impaired deformability was seen in humans,¹⁸ rats,¹⁸ and rabbits with iron deficiency anemia²⁶ and in stored RBCs from healthy human donors.²⁷ Rigid RBCs are less able to pass through previously negotiable microcirculatory beds and are more prone to undergo extravascular hemolysis in the spleen.²⁸ Indeed, circulatory RBC lifespan is decreased in humans with iron deficiency anemia^{16,29-31} and in relevant animal models.^{26,32} In humans, decreased circulatory lifespan is most likely due to extravascular hemolysis in the spleen²⁹⁻³¹ and is corrected by iron repletion.^{16,30}

Remarkably, in several older studies,^{16,29,33} RBCs obtained from donors with iron deficiency anemia were transfused into healthy recipients, without prior refrigerated storage. In each study, the transfused iron-deficient RBCs had a decreased circulatory lifespan/recovery, most likely due to splenic clearance. In addition, when RBCs obtained from healthy donors were transfused into recipients with iron deficiency anemia, the transfused RBCs had a normal lifespan, suggesting that the iron deficiency-induced defect was intrinsic to the RBC and not due to enhanced clearance mechanisms.^{33,34}

Iron deficiency decreased the 24-hour post-transfusion RBC recovery in a mouse model. Replicating the human studies described just above from the 1940-70's is no longer ethically permissible. Although the RBCs transfused in these studies were from donors with iron deficiency anemia, not from donors with iron-deficient erythropoiesis, deliberate allogeneic human transfusion studies using such donors and healthy volunteer recipients are no longer feasible. Instead, we used a mouse model to obtain proof-of-principle preliminary data. Three mouse donor cohorts were prepared: iron replete, iron-

deficient erythropoiesis, and iron deficiency anemia (Fig. 3). Similar to our prior studies,³⁵ refrigerator-stored, transfused RBCs from iron-replete donors had a normal 24-hour post-transfusion recovery (mean 77.1%). In addition, as expected from other publications,^{16,29,33} the 24-hour post-transfusion recovery was poor using RBCs from donors with severe iron-deficiency anemia (mean 46.7%; $p<0.001$). In contrast, results using donors with iron-deficient erythropoiesis were subnormal (mean 66.5%; $p<0.05$) and would be less than the FDA-mandated minimum (in this mouse model). Taken together, **these data support our hypothesis that, after refrigerated storage, RBCs from donors with iron-deficient erythropoiesis without anemia are suboptimal.**

2. Objectives

2.1 Primary Hypothesis

- 1) The 24-hour post-transfusion RBC recovery of units obtained from donors exhibiting iron-deficient erythropoiesis will not meet FDA standards for clinical use.
- 2) The 24-hour post-transfusion RBC recovery of units obtained after intravenous iron repletion will improve significantly and will meet FDA standards for clinical use.

2.2 Secondary Hypothesis

- 1) The extent of iron-deficient erythropoiesis, as measured by RBC zinc protoporphyrin levels, will predict the 24-hour post-transfusion RBC recovery.
- 2) There will be a good correlation ($R^2 > 0.5$) between RBC zinc protoporphyrin levels and other markers of iron status: ferritin, hepcidin, soluble transferrin receptor, reticulocyte hemoglobin.
- 3) Iron repletion will improve fatigue score³⁶ and self-reported health and wellbeing score.³⁷
- 4) Iron repletion will decrease RBC zinc protoporphyrin and soluble transferrin receptor levels.
- 5) Iron repletion will increase hepcidin, ferritin, and hemoglobin levels.
- 6) Iron repletion will improve the following neurocognitive scores:
 - a) Cognitive Function Composite Score
 - b) Executive Function
 - c) Attention
 - d) Episodic Memory
 - e) Language
 - f) Processing Speed
 - g) Working Memory
- 7) Iron repletion will improve the following emotional well-being scores:
 - a) quality of life
 - b) fatigue
 - c) depression
 - d) anxiety
- 8) Metabolite levels in the RBC unit will correlate with iron status and 24-hour post-transfusion RBC recovery.

3. Study Population

3.1 Enrollment Inclusion Criteria:

- 1) 18-75 years old;
- 2) healthy (by self report);

- 3) body weight >110 lbs;
- 4) female hematocrit >38%, male hematocrit >39%;
- 5) frequent blood donor (men ≥ 2 and female ≥ 1 RBC unit donations in past year);
- 6) ferritin <15 ng/mL;
- 7) zinc protoporphyrin >60 μ mol/mol heme.

3.2 Enrollment Exclusion Criteria:

- 1) ineligible for donation based on the New York Blood Center donor autologous questionnaire;
- 2) C-reactive protein >10 mg/L;
- 3) sickle cell trait (by self report);
- 4) systolic blood pressure >180 or <90 mm Hg, diastolic blood pressure >100 or <50 mm Hg;
- 5) heart rate <50 or >100;
- 6) temperature >99.5°F prior to donation (attempts will be made to reschedule donation if possible);
- 7) temperature >100.4°F or subjective feeling of illness prior to ^{51}Cr 24-hour RBC recovery study (to avoid the subject having a concurrent illness that may affect post-transfusion recovery); (attempts will be made to reschedule donation and ^{51}Cr 24-hour RBC recovery study);
- 8) positive results on standard blood donor infectious disease testing;
- 9) pregnancy;
- 10) taking, or planning to take, iron supplements and not willing to stop for duration of study;
- 11) history of severe asthma requiring hospitalization, allergic eczema (atopic dermatitis), or other atopic allergy causing anaphylaxis.

4. Trial Enrollment

4.1 Screening/Recruitment

The New York Blood Center study staff will send a recruitment letter/email (see Appendix 1) to potential subjects who are 18-75 years old and frequent blood donors donating in the Manhattan catchment area. We will define frequent blood donors as (1): men who have donated the equivalent of at least 2, and women who have donated the equivalent of at least 1, RBC units in the past year.

Volunteers responding to the recruitment email will be screened for participation in the study by phone or email (see Appendix 7 for all screening forms) and then invited for a

screening meeting (P&S 14-434) to confirm eligibility and provide informed consent.

Screening day (P&S 14-434): All volunteers will be given the health questionnaire they would receive upon donation at the New York Blood Center (see Appendix 7). All volunteers who decide to proceed with screening and sign consent will have four tubes of blood drawn to determine baseline laboratory values and to perform a blood type and antibody screen. If the baseline hematocrit is >38% (female) or >39% (male), ferritin < 15ng/mL, zinc protoporphyrin level is > 60 umol/mol heme, and C-reactive protein is <10mg/L (see inclusion/exclusion criteria above) then the volunteer will be scheduled for an autologous whole blood donation at the New York Blood Center, and scheduled for an autologous 51-Chromium red cell recovery study 6 weeks after donation. At that time, neurocognitive assessments and emotional wellbeing will be performed as well (see Appendix 2-5 for surveys and section 5.4). Re-screening: Those subjects who meet the ferritin <15ng/mL and the zinc protoporphyrin > 60umol/mol heme criteria, but do not qualify due to a low hematocrit may be re-screened between 2 weeks to 3 months later.

4.2 Randomization

Randomization will be performed using a computerized system with equal allocation (1:1) to iron repletion or placebo. Randomization will be stratified by gender; randomly permuted block sizes of 4, 6, or 8 will be used. The moment of randomization will be recorded and will occur only after successful completion of the first post-transfusion RBC recovery study (i.e., between Day #43-71; target is the day after the post-transfusion recovery study; performed on Harkness Pavilion 10). Volunteers will be admitted to the Columbia General Clinical Research Center (GCRC) (supported by the Columbia Clinical and Translational Science Award (CTSA)). One peripheral intravenous line will be inserted and blood (2 tubes, 10mL) will be drawn for determining the 24-hour post-transfusion recovery. The subject will be randomized at this point. The randomization scheme will be created by a statistician unaffiliated with the study team and provided to the research pharmacy and DSMB prior to study initiation. The CUMC research pharmacy will be responsible for randomizing each subject to the appropriate treatment arm and will prepare either the iron treatment or saline placebo and provide it to the study team in a blinded

fashion. If a subject arrives on the day of randomization and has a fever ($T>100.4F$) or feels ill, then the 24-hour post-transfusion recovery sample will be drawn, but randomization may be held until the subject feels better and reschedules.

4.3 Blinding

The randomized group will only be known to the Columbia University Medical Center Research Pharmacy and the statistician who generated the randomization scheme. The study will be double-blind. As described in section 5.3, both a test dose of the iron treatment/placebo and the treatment/placebo will be blinded. The test dose will be administered prior to giving the full dose to ensure safety of treatment. A research pharmacist will provide the placebo (IV saline) or treatment (IV low molecular weight iron-dextran or ferric carboxymaltose) and test dose of iron/placebo in a tinted infusion bag and tubing specifically designed to maintain blinding in clinical research studies (Medipak). A research nurse unaffiliated with the study team, from the Outpatient or Inpatient Center at the Columbia General Clinical Research Center (Harkness Pavillion 10th Floor), will be responsible for the test infusion and total dose iron infusion. With this design, volunteers and study investigators will be blinded to whether volunteers receive the active intervention or placebo. Subjects in both groups will receive similar discharge instructions as if they had received low molecular weight iron-dextran (see Appendix 6 for discharge instructions). Only the research pharmacist and the statistician on the DSMB will not be blinded. Scheduling and logistic communications with volunteers will be made by the study coordinator, who will also be blinded to the treatment group. The research pharmacy will provide a standard 1-gram dose of low molecular weight iron-dextran, ferric carboxymaltose, or saline in special bags designed to conceal group assignment.

Situations may arise in which breaking the blind earlier would be in the best interest of the volunteer. In any situation in which a physician or the subject asks to be un-blinded to study treatment, a sealed copy of the randomization scheme for each subject will be kept in the investigator's office and will be broken upon request. Furthermore, the research pharmacy can be reached on an emergency basis to provide this information. Finally, any un-blinding that occurs will be reported to the DSMB and ultimately reported in the resulting publication.

5. Interventions

5.1 Blood Donation:

The blood donation will be performed at the New York Blood Center at [name] per standard protocol for autologous RBC donations. A urine pregnancy test will be performed on all female participants < age 55 on the day of donation. A positive pregnancy test will result in exclusion from the study (see Appendix 7 for donation day eligibility form). At the New York Blood Center, subjects will be screened per the standard protocol for autologous RBC donations. This will include health questionnaire, finger stick hemoglobin determination, temperature, heart rate and blood pressure measurement. Following donation, the blood will be leukoreduced, packed, and stored in AS-3 solution. The unit will be transferred to the CUMC-NYPH blood bank for storage following standard hospital procedures.

5.2 ^{51}Cr 24-hour post-transfusion RBC recovery study

Volunteers will be admitted to the Columbia General Clinical Research Center (GCRC) (supported by the Columbia Clinical and Translational Science Award (CTSA) on Harkness Pavilion 10). A urine pregnancy test will be performed on all female participants < age 55 years on the day of infusion. A positive pregnancy test will result in exclusion from the study (see Appendix 7 for infusion eligibility form). Two intravenous lines will be placed in contralateral arms. Four tubes of blood will be drawn to determine laboratory values and to perform a repeat blood type and antibody screen. If the subject chooses to come in for an optional blood draw within 30 days of this study visit, only three tubes will be drawn as the type and screen will not be necessary.

A 30 mL aliquot of the autologous blood unit donated 6 weeks prior will be removed using sterile technique by a licensed radiopharmacist into a syringe. This syringe will be labeled with the volunteer's identifying information per hospital policy and radiolabeled in the Kreitchman PET Center. The radiolabeling will be performed using 20 microcurie of sodium chromate (^{51}Cr) based on the methods of Moroff et al⁴ and the recommendations from the International Committee for Standardization in Hematology.³⁸ The ^{51}Cr labeled red cells will be washed with saline and then infused intravenously

(over 1 minute through one IV line) into the volunteer. For calculating counts per minute per ml of RBC at time zero (T0), samples (two tubes, 10 mL) from the contralateral arm will also be obtained after 5, 7.5, 10, 12.5, 15 minutes, 30 minutes, and 1-hour after infusion. Thus, in total, the volunteers will be infused approximately 30mL of packed radiolabeled RBCs and will have 16 tubes or 80 mL of blood drawn overall (8 time points x 2 tubes x 5mL per tube = 80 mL). All blood draws will be performed from the peripheral intravenous line to avoid multiple needle sticks. Finally, because 30mL of blood will be infused and only 80mL of blood removed, this will leave the volunteer with a net loss of only 50mL of blood on the day of infusion. Following the 1-hour timed blood draw, the subject will be discharged.

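### Section 4.3 lets a bare request from a physician or the subject open the treatment code, which puts the blind at risk for the self-reported and cognitive outcomes

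*Combined protocol and SAP*

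**What the plan says.** Section 4.3 (Blinding) restricts knowledge of the arm: "The randomized group will only be known to the Columbia University Medical Center Research Pharmacy and the statistician who generated the randomization scheme". It calls the study double-blind and supports this with tinted bags and tubing, an infusion nurse from outside the study team, and a blinded coordinator.

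It then turns to code breaks. The introduction is "Situations may arise in which breaking the blind earlier would be in the best interest of the volunteer". The operative rule follows. Its trigger is worded as "In any situation in which a physician or the subject asks to be un-blinded to study treatment". The stated consequence of such a request is that "a sealed copy of the randomization scheme for each subject will be kept in the investigator's office and will be broken upon request". There is a second route: "the research pharmacy can be reached on an emergency basis to provide this information". The section closes with a safeguard: "any un-blinding that occurs will be reported to the DSMB and ultimately reported in the resulting publication".

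Section 4.2 has a statistician outside the study team create the scheme and the research pharmacy randomize each subject. Section 11.1 makes the primary analysis intent-to-treat.

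**The concern.** The operative rule is triggered by a request alone. It does not require that knowing the treatment would alter the subject's care. It names nobody to approve the request and does not say who may learn the answer. The best-interest sentence explains why the rule exists but is not written as a condition of it. Taken literally, a volunteer who is merely curious has the code opened at any time after randomization.

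Requests are plausible. Subjects are selected for iron deficiency (Section 3.1) and must forgo iron supplements for the duration (Section 3.2, exclusion 10). Section 9.2 accepts that placebo subjects may have adverse events from continued deficiency and encourages participants to call about new or changed symptoms.

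Two things are at stake. First, a subject who knows the arm can answer questionnaires, or put effort into tests, accordingly. Second, a subject who learns of a saline assignment has a reason to start iron or leave. That would dilute the primary contrast or select who reaches the second recovery study.

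**Working it through.** **1. The statements side by side (all Section 4.3)**

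| Element | What the text provides |
|---|---|
| Who knows the arm | Pharmacy and the generating statistician |
| Stated purpose of early unblinding | The volunteer's best interest, as introduction |
| Trigger | A request by a physician or the subject |
| Care-need test, approver, limit on recipients | None stated |
| Location of code | Sealed per-subject copy in the investigator's office, plus the pharmacy in an emergency |
| After the event | Report to DSMB and in the publication |

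The last row acts only once the blind has been broken. Nothing in the other rows filters requests.

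**2. Which outcomes follow the exposure**

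Section 6.1 schedules surveys and cognitive tests before each donation and each recovery study. Those after infusion are at the second donation (5 months ± 4 weeks) and the second recovery study (40 to 42 days later). Taking 5 months as about 152 days:

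- Earliest second recovery study: 152 − 28 + 40 = 164 days, or 5.4 months.
- Latest: 152 + 28 + 42 = 222 days, or 7.3 months.

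The four questionnaires are self-administered (Section 5.4.2), and cognitive scores depend on effort. The primary outcome, ⁵¹Cr recovery, is a laboratory measure, so it can be affected only through what subjects do after learning the arm.

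**3. Illustration for the primary outcome**

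Inputs from Section 11.2: difference 4 points, SD 5.0, alpha 0.05 two-sided, power 0.80, 26 per arm, 30 per arm randomized.

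The plan's own figure reproduces. With a standardized effect of 4/5 = 0.8, a two-sample t-test needs 25.5 per arm, which rounds up to 26. Power is 80.7% at 26 and 86.1% at 30.

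Let q be the proportion of placebo subjects who unblind on request and then take iron with the full effect of the study treatment. The expected difference is 4 × (1 − q).

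| q (assumed) | Difference | Power, 26 per arm | Power, 30 per arm |
|---|---|---|---|
| 0% | 4.0 | 80.7% | 86.1% |
| 5% | 3.8 | 76.6% | 82.5% |
| 10% | 3.6 | 72.1% | 78.3% |
| 20% | 3.2 | 61.9% | 68.4% |

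The SD is held at the plan's 5.0 and interim looks are ignored. The rates are assumptions, because the documents give none. Full effect for every crossover is the worst case. The 26 column assumes the dropout allowance is fully used; the 30 column assumes nobody is lost.

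**4. Does it reach later allocations?**

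Random blocks of 4, 6 or 8 (Section 4.2) were simulated for a stratum of 30, with the sizes assumed equally likely. If 0%, 5%, 10% or 20% of earlier allocations are revealed, the next is guessed correctly about 50%, 51%, 52% or 53% of the time. Occasional code breaks add little predictability.

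**The case against.** The strongest reply is that the rule follows directly on the best-interest sentence and can be read as confined to those situations. That reading is available, but the operative sentence does not carry the condition, and a site has to act on that sentence. The ambiguity is itself a reason to amend.

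Several other points on that side stand:

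- The copies are sealed, so holding them unblinds nobody.
- Every unblinding must be disclosed, and intent-to-treat is already specified.
- Exclusion 10 removes volunteers unwilling to stop iron supplements. Section 11.1 already expects some placebo crossover and plans a regression on zinc protoporphyrin.
- Five of the eight secondary hypotheses in Section 2.2 (1, 2, 4, 5 and 8) concern laboratory measures only, so the direct bias is confined to the subjective and cognitive scores.
- The power figures depend on assumed rates and worst-case crossover. At 30 per arm, the 10% case falls only about 2 points below the planned 80%.

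A reader might go further and infer that allocation concealment is compromised. The documents do not support this. Section 4.3 makes no such claim; its wording about concealing group assignment describes the infusion bags. Concealment rests on Section 4.2, and unblinding a subject comes after that subject's allocation. A residual risk would exist only if copies for subjects not yet randomized were kept in the office, which the text does not settle.

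**Conclusion.** The concern holds as a weakness in a stated rule. As written, a request is enough to end the blind for a subject, and disclosure afterwards does not restore it. The main exposure is the self-reported and cognitive outcomes at the second donation and second recovery study. Its size there cannot be calculated from the documents.

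For the primary outcome the exposure is indirect and of unknown frequency. Under the assumed 5% to 20% full-effect crossover, the loss of power is about 4 to 19 percentage points at 26 per arm (80.7% to between 76.6% and 61.9%) and about 4 to 18 at 30 per arm (86.1% to between 82.5% and 68.4%). These figures illustrate the mechanism and are not a forecast.

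It would be too strong to conclude that the trial is not double-blind. Masking remains for every subject for whom nobody asks. The change should be made, but it is not grounds for rejecting the design.

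**What to change.** Amend Section 4.3:

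1. Before a subject's final blood draw after the second recovery study, open the code only when a clinician states that knowing the treatment is needed for that subject's care. Release the result to that clinician and not to blinded study staff.
2. Answer a subject's own request to know after that subject's final draw.
3. Extend the existing DSMB and publication reporting to give the date and reason for each unblinding.
4. Keep the intent-to-treat analysis as primary. Add a sensitivity analysis of the subjective outcomes that excludes scores obtained after unblinding. It is supportive only, since unblinding occurs after randomization and may be related to symptoms.
5. Preferably, hold the sealed copies with the research pharmacy or another unblinded party, provided the pharmacy's emergency access is continuous. The documents do not state its hours. Removing the office copies closes one of two access routes, so this must be confirmed first.

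The cost is a short amendment and one added analysis. The real downside falls on subjects without a care need, who wait until the last visit, possibly more than seven months after infusion, to learn what they received.
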